Alcohol has multiple biological effects on the nervous system which each represent potential targets for pharmacotherapy of alcohol use disorders. Animal studies indicate that alcohol induced generation of GABA_A receptor neuroactive steroid agonists mediate several of alcohol's effects. Pharmacologic blockade of neuroactive steroid production has been reported to reduce alcohol intake in animal models. Dutasteride, a widely used medication to treat benign prostatic hypertrophy is an irreversible inhibitor of 5-alpha reductase (5AR) enzymes required for the production of neuroactive steroids, and thus has potential as a pharmacologic treatment for alcohol use disorders in humans. In a recently completed placebo controlled study in humans of the effects of a single 4 mg dose of dutasteride given 2-4 days prior to a moderate dose of alcohol (0.8 gr/kg body weight) we found that while dutasteride has limited effects on subjective responses to a standard battery of alcohol effect questionnaires, it produced a significant reduction in drinking during the first two weeks following dutasteride, but not placebo medication treatments for subjects with a history of moderate drinking. The proposed study will extend these findings by examining the safety and efficacy of dutasteride for alcohol use disorders in human subjects by conducting a 12-week randomized placebo controlled trial of dutasteride for the reduction of alcohol use in male problem drinkers.

Aim 1. To examine the safety and efficacy of dutasteride in helping problem drinkers to reduce or stop drinking. 160 men with hazardous levels of alcohol use (≥ 24 standard drinks / week) will be randomly assigned to treatment with either dutasteride or placebo for 12-weeks. Alcohol use will be reported daily via an interactive voice response system. Biological markers (gamma glutamyl transferase, carbohydrate deficient transferin) will be used as secondary measures of change in alcohol use and a serum neuroactive steroid metabolite 3 α -androstaneadiol glucuronide will be used to monitor inhibition of 5 α -reductase enzyme activity by dutasteride. We hypothesize that 1 mg / day dutasteride will be well tolerated by heavy drinkers, will produce $\geq 85\%$ reduction in serum markers of 5 α -reductase enzyme activity and that compared with placebo will result in a greater reduction in the number of heavy drinking days and drinks per week.

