Subjects: 39 subjects were randomized to study medication or placebo, 36 have completed 8 weeks of medication. Participants enrolled in the study averaged 52.7 ± 8.9 (s.d.) years of age, 82% of whom met criteria for AD and consumed on average of 46 ± 20 (s.d.) SDs / week with 5.1 ± 1.9 (s.d.) HDD / week at study entry. 50% of subjects had a family history of alcohol dependence and 73% identified a goal of reducing drinking while 27% identified a goal to stop drinking.

Safety: Study medication has been well tolerated with similar rates of side effect reports for dutasteride vs. placebo during the 8-week medication treatment phase [mean number of side effects reported / subject: dutasteride= 6.0 ± 5.8 (s.d.) vs. placebo= 8.4 ± 10.8 (s.d.)]. The number of subjects reporting a sexual related side effect was also been similar between the two arms ($n=3$ for dutasteride and $n=4$ for placebo). Three subjects dropped out of treatment during the 8-week active phase (2 placebo, 1 active drug) and none due to medication side effects. Participation in completing daily self-reports was high [$90\% \pm 10$ (s.d.) of possible reports].

Laboratory measure of drug effect for the first 15 subjects showed a significant reduction in serum 3 α -diolG for subjects randomized to dutasteride ($n=9$) at both 4-weeks (84% reduction; $p=0.003$) and 8-weeks (86% reduction; $p=0.002$) demonstrating effective inhibition of 5AR activity with the dutasteride dosing schedule proposed. There was no effect of dutasteride on serum testosterone levels at either 4- or 8-weeks ($p=0.42$ and 0.15 respectively) in this sample of heavy drinkers which mirrors the lack of effect of dutasteride on serum testosterone in other samples (Clark et al. 2004). There was no significant change in serum 3 α -diolG or testosterone in subjects in the placebo group ($n=6$).

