Drinking outcomes: For 27 subjects completing the 8 week active phase as of July 1 (excluding 7 subjects with abstinence from outset (3 dutasteride and 4 placebo subjects) mixed model analysis showed a main effect of baseline drinking ($p=0.005$), study week ($p=0.001$), AKR1C3*2 genotype ($p=0.029$) and a trend for genotype by drug interaction ($p=0.56$) such that subjects gradually reduced drinking during the 8 weeks with AD risk allele homozygotes showing the highest level of drinking and the greatest benefit from dutasteride compared with placebo condition. For the 19 subjects who have reaced the 2 month post-treatment follow-up there was a significant drug x time interaction with a 48% decrease in SDs/w for dutasteride and a 39% decrease for placebo compared with baseline drinking [mixed model $F(124)=4.68$, $p=0.032$; effect size $d=0.30$].

Summary. These pilot study results support our ability to recruit and enroll subjects for the proposed study and indicate that dutasteride is well tolerated in alcoholic subjects with no effect of dutasteride on serum testosterone levels in the face of an 85% reduction in the 5AR enzyme metabolite 3 α -diolG. Preliminary

drinking outcomes indicate that participants reduced drinking during the study period and that dutasteride may have greatest benefit for AKR1C3*2 alcohol dependence risk C-allele homozygotes.

C.2. RESEARCH DESIGN AND METHODS

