General Design: This study employs a parallel-groups design in which dutasteride is compared with placebo to evaluate its safety and efficacy in reducing the likelihood of drinking and of heavy drinking by problem drinkers. The study will be conducted in the UCHC Department of Psychiatry Clinical Research & Evaluation Unit (CREU) and the Clinical Research Center (CRC). Random assignment to treatment group and double-blind conditions will be maintained throughout the study. The study will be conducted in three consecutive phases: a 1 to 2 week pre-treatment assessment period, a 12-week treatment period, and a 6-month post-treatment follow-up period. Patients will be provided medical management including brief counseling (adapted from Pettinati et al. 2004) at each treatment visit. Daily reports will limit retrospection bias during the treatment period. Objective laboratory data (serum GGT and %dCDT) will be used to further corroborate patient reports. Data obtained during the post-treatment follow-up period will make it possible to evaluate the durability of treatment effects beyond the period of active treatment.

Patients: Male drinkers who want to reduce or stop drinking will be recruited using advertisements in local media (including text ads in newspapers and weekly community circulars, radio ads on local radio stations, web ads on internet sites and web postings on community message boards), by posting/distributing recruitment materials at area Colleges and Universities, and in community settings with public posting areas (such as hospitals, town halls, public libraries, YMCA, health fairs/organizations), and by referral from UCHC medical clinics where screening for alcohol use problems using the NIAAA Screening, Brief Intervention, and Referral for Treatment (SBIRT) protocol

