effects derived from prior studies of dutasteride (any ongoing potential medication side effects reported at the 2-month follow-up will be assessed again at 4- and 6-month follow-up visits as needed).

d. Measures of treatment received: Records of all medication taken will be recorded. The study staff will also record the number of contact hours subjects have been exposed to for any treatment outside of the study that is related to their drinking to identify if this variable might need to be considered as a covariate in outcomes analysis.

C.6.b.4. Areas assessed at intake, midpoint, end of treatment and at follow-up visits:

a. Alcohol-related problems: The Short Inventory of Problems (SIP). The SIP is a 15-item instrument derived from the Drinker Inventory of Consequences (DrInC), which was developed for use in Project MATCH as a measure of alcohol-related consequences.

b. Psychological symptoms: a) The Beck Depression Inventory (BDI), a 21-item self-report measure of depressive symptoms, yields a total score that ranges from 0 to 63 (Beck et al. 1961). The BDI is generally regarded as a sensitive self-report measure of depressive symptoms, and will be used to explore the relation between depressive symptoms and treatment. b) The State version of the Spielberger State-Trait Anxiety Inventory (STA), a 20-item self-report questionnaire (Spielberger 1983), will be used to provide concomitant monitoring of anxiety symptoms.

c. Drinking Motives: Drinking motives will be measured with the Drinking Motives Questionnaire [DMQ; (Cooper et al. 1992; Cooper 1994)] to explore potential changes as a result of treatment in drinking motives. This instrument contains 20 items with 4 subscales, drink to a) cope motives (e.g., "Because it helps when you are feeling nervous or depressed"), b) conformity motives (e.g., "Because it helps me fit in"), c) enhancement motives (e.g., "Because it's fun"), and d) social motives (e.g., "Because it makes a social occasion more enjoyable"). The DMQ will be administered at baseline and for those subjects who continue to drink again at midpoint, end of treatment and at the 2,4, and 6-month follow-up visits.

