d. Alcohol outcome-expectancies will be assessed with 24 items from the Alcohol Effects Questionnaire [AEQ; (George et al. 1995)] probing 4 positive expectancy subscales (social and physical pleasure, aggression and power, social expressiveness, and relaxation and tension reduction) and 1 negative subscale (cognitive/physical impairment) to explore potential changes as a result of treatment with dutasteride. The AEQ will be administered at baseline and for those subjects who continue to drink again at midpoint, end of treatment and at the 4 and 6-month follow-up visits.

e. Integrity of the double blind: A Medication Questionnaire (MED-Q) will be completed by the subject at the end of treatment (or at the time of treatment discontinuation for subjects who do not complete the 12-week treatment period). It includes an indication of which medication group the subject believes to have been in, their level of confidence in that assessment and the reasons for coming to that conclusion.

C.6.b.5. Methodological Problems in Daily Monitoring:

i. Daily Recording: A research assistant will monitor the IVR call generated dataset regularly to review whether subjects are supplying daily responses and if not that problems and questions are promptly addressed. Subjects who fail to call in during the allotted time receive a computerized reminder call [which has been shown to increase the response rate by nearly 10% (Kranzler et al. 2004)]. Monetary incentives will be used to encourage subjects to make calls daily. Subjects will be paid \$1 for each telephone call completed and an additional \$3 for each week in which they complete all calls, to a maximum of \$120 (\$10 per week for 12 weeks). Although this is less than is paid for daily reporting in other studies, we have found that subjects in treatment studies do not require the same level of incentives to promote adherence to daily reporting as is the case for studies in which no other benefits accrue to participation.

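### After baseline the AEQ goes only to men who continue to drink, so any comparison of arms on this exploratory scale is conditioned on an outcome the drug is meant to change

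*Combined protocol and SAP*

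**What the plan says.** Section C.6.b.4.d introduces the AEQ, with four positive expectancy subscales and one negative, "to explore potential changes as a result of treatment with dutasteride". After baseline it is given "for those subjects who continue to drink again at midpoint, end of treatment and at the 4 and 6-month follow-up visits". The plan does not define continuing to drink: it gives no time window and no data source.

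Section C.6.b.4.c sets the same kind of rule for the Drinking Motives Questionnaire (DMQ): "The DMQ will be administered at baseline and for those subjects who continue to drink again at midpoint".

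Stopping is among the intended effects of treatment. Aim 1 is "To examine the safety and efficacy of dutasteride in helping problem drinkers to reduce or stop drinking", and the General Design paragraph in C.2 says the trial will "evaluate its safety and efficacy in reducing the likelihood of drinking and of heavy drinking by problem drinkers".

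Section C.8 lists the primary and secondary outcomes and their models. Neither the AEQ nor the DMQ is listed, and neither has an estimand, a model or a rule for missing scores. Table 1 shows both instruments without the drinking restriction, but does not say that abstainers complete them. It places the AEQ at V1, V8, V10 and V11 only, whereas C.6.b.4.d also names the midpoint.

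**The concern.** The AEQ's stated purpose is causal: change brought about by dutasteride. Randomisation supports that reading only if the men measured later are all the randomised men, or a subset chosen without regard to what happened after randomisation. Here the subset is chosen by drinking status during or after treatment.

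If more men stop in one arm, or if a different kind of man stops, the continuing drinkers in the two arms are no longer comparable. Suppose heavier drinking propensity goes with stronger positive expectancies. The arm with more abstainers would then keep drinkers with higher average scores, even if the drug had no effect on expectancies.

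Whatever happens by arm, abstainers contribute no later score, and a score that was never collected cannot be recovered at analysis.

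**Working it through.** **1. The plan's own figure.** C.8.b states 80% power with 80 completers per arm for d = 0.45 at alpha 0.05. Sidedness is not stated; two-sided is assumed. In the normal approximation, power = Phi(d × sqrt(n/2) − 1.96) = Phi(0.45 × sqrt(40) − 1.96) = Phi(0.886) = 81%. The stated figure reproduces. It concerns the main efficacy comparison; the plan gives no figure for the AEQ, so it serves here only as a yardstick.

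**2. How many men might go unmeasured.** The pilot report (C.1.c) describes 27 completers, "excluding 7 subjects with abstinence from outset (3 dutasteride and 4 placebo subjects".
- If the 27 are those left after exclusion: 7/(27 + 7) = 7/34 = 21%.
- If the 27 include the 7: 7/27 = 26%.

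The arm denominators for these men are not given, so 3 and 4 are counts, not rates. On goals, "73% identified a goal of reducing drinking while 27% identified a goal to stop drinking". The abstinence that would count in the trial could be higher or lower than in the pilot, because continuing to drink is undefined.

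**3. Loss of information when abstinence is equal by arm.**

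| Abstinent | Re-measured per arm | Power for d = 0.45 |
|---|---|---|
| 0% | 80 | 81% |
| 21% | 80 × 0.79 ≈ 64 | Phi(0.45 × sqrt(32) − 1.96) = Phi(0.586) ≈ 72% |
| 26% | 80 × 20/27 ≈ 59 | Phi(0.490) ≈ 69% |

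At 21% the difference detectable with 80% power rises to about 0.50 SD. These are unadjusted comparisons among completers.

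**4. Bias when abstinence differs by arm.** The documents give no inputs for this, so all of them are assumptions. Let drinking propensity and AEQ score be standard bivariate normal with correlation r. A man is re-measured if his propensity exceeds the cut-off c that leaves a share k of his arm. The mean score among those re-measured is then r × phi(c)/k.

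| Share kept, k | phi(c)/k |
|---|---|
| 0.85 | 0.274 |
| 0.80 | 0.350 |
| 0.70 | 0.497 |

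False arm difference with no drug effect on the scale:
- 20% vs 30% abstinent: r × (0.497 − 0.350) = 0.147r, which is 0.03 SD at r = 0.2 and 0.07 SD at r = 0.5.
- 15% vs 30% abstinent: r × (0.497 − 0.274) = 0.223r, which is 0.04 SD at r = 0.2 and 0.11 SD at r = 0.5.

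The range is 0.03 to 0.11 SD. With 20% vs 25-40% abstinent instead, the same model gives 0.015 to 0.15 SD.

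**5. Size against sampling error.** With 80 completers per arm, 20% vs 30% abstinent leaves 64 and 56 men, and the standard error is sqrt(1/64 + 1/56) = 0.18 SD. With 15% vs 30% it leaves 68 and 56, again 0.18 SD. The bias is thus about 0.03/0.18 ≈ 0.2 to 0.11/0.18 ≈ 0.6 of a standard error.

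Simulated type I error for a two-sample t-test (6,000 trials per scenario, 80 per arm before selection):
- 20% vs 20%, r = 0.3: 5.0%
- 20% vs 35%, r = 0.3: 6.8%
- 20% vs 35%, r = 0.5: 10.1%
- 20% vs 40%, r = 0.5: 12.8%

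**The case against.** The strongest reply is that no comparison of arms on the AEQ is specified. The plan speaks of exploring change, C.8 assigns the scale no test, and no listed conclusion rests on it. That stands. The comparison is implied by the stated purpose, and the point is confined to what an exploratory analysis could support.

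Second, the only evidence in the documents on abstinence by arm is 3 dutasteride and 4 placebo men, which shows no excess on the drug. Those men were abstinent from the outset, so their abstinence may reflect a goal of stopping rather than a response to treatment. That stands too. The unequal rates used above are assumptions, and so is the correlation.

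Third, the DMQ asks why a man drinks, so restricting it to drinkers is natural. This is accepted, and no change in who receives the DMQ is proposed. The argument does not carry over to the AEQ, which asks for beliefs about alcohol that an abstinent man can report.

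A reader might also infer that the rule removes the best responders. The documents do not support this. Selection is on any drinking versus none, the Aim 1 hypothesis concerns heavy drinking days and drinks per week, and most pilot men aimed to reduce. A man who cuts down sharply but still drinks is re-measured.

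**Conclusion.** The point holds for the AEQ as a low-severity design improvement. Follow-up scores depend on a post-randomisation outcome that treatment is meant to affect, and neither C.8 nor Table 1 repairs this.

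The firmer cost is lost information: about 16 of 80 men per arm if abstinence resembles the pilot's 21%, with power for d = 0.45 falling from 81% to 72%. Bias is possible but not shown. It is zero if abstinence is equal and the same kind of man abstains in each arm. It is 0.03-0.11 SD if 15-20% versus 30% abstain and the correlation is 0.2-0.5.

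It would be tempting to conclude that the plan contains a biased treatment comparison. The documents do not go that far, because no such test is written and no arm difference in abstinence has been shown. Primary, secondary and safety conclusions are untouched.

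**What to change.** In C.6.b.4.d, delete the restriction to continuing drinkers and give the AEQ to all randomised men at each visit where it is scheduled. First reconcile that section, which includes the midpoint, with Table 1, which shows V1, V8, V10 and V11 only. State that any comparison of arms on the AEQ uses all men, adjusted for baseline AEQ.

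Keep the DMQ restricted to drinkers. Define continuing to drink (time window and data source), report the DMQ descriptively as conditional on drinking, and give the number re-measured by arm.

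The cost is a few minutes for abstinent men at visits they already attend. The change has to be made in data collection.

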d. *Daily Events:* Participants will be asked whether they experienced a list of nine possible daily events (3 stressful, 3 pleasant, and 3 situations where someone might drink). These measures will be used to assess the influence of positive and negative events on drinking.

e. *Daily medication usage:* Using IVR, subjects will report daily medication use. Additionally, at each bi-weekly study visit, subjects will be asked by the study staff to indicate the number of study drug capsules taken each day. This method has been shown to be highly correlated with electronic monitoring of medication adherence (Feinn et al. 2003).

C.6.b.3. Areas assessed biweekly during the active treatment period and follow up visits:

a. *Alcohol use patterns:* The TLFB (Sobell and Sobell 1992) will be used to estimate drinking at intake, at each biweekly study visit during the active treatment period and at each of the two follow-up evaluations. This interview procedure will provide quantity/frequency of alcohol consumption data for each day during the period prior to the interview. We will also be collecting daily measures of alcohol consumption using IVR during the active treatment period because despite evidence of the reliability and validity of the TLFB when used by trained interviewers, the TLFB is less useful for detecting patterns of alcohol consumption that vary on a day-to-day basis (Carney et al. 1998; Searles et al. 2000). Daily IVR reports will also enable us to examine co-variation in daily mood and daily events with alcohol use in order to address whether dutasteride moderates associations between daily mood or daily events and drinking as our group has found using IVR methods for treatment with naltrexone (Kranzler et al. 2004; Armeli et al. 2006).

b. *Alcohol Craving:* The Penn Alcohol Craving Scale (PACS) is a 5-item self-report measure that includes questions regarding the frequency, intensity, and duration of craving over the past week as well (Flannery et al., 1999). The PACS has been shown to predict subsequent drinking during alcohol treatment trials (Flannery et al., 1999, 2003).

c. *Medication adverse effects:* Subjects will provide reports of side effects at each bi-weekly phone visit and study visit during the active treatment phase and 2-month follow-up visit using a list of adverse medication

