C.8.a.1. Safety: Safety will be analyzed using categorical outcomes, defined by the type and severity of adverse effects. Summary measures of adverse events (AEs) will be developed by organ system from the adverse event checklist and will be compared for patients receiving dutasteride or placebo using χ^2 analysis. Comparisons will be conducted on 1) the number of patients in each of the two groups who report AEs, 2) the number of patients in each of the two groups who report moderate-to-severe AEs, and 3) the number of patients in each group who discontinue treatment due to AEs. Individual AEs that occur in $\geq 5\%$ of patients in either medication condition will be examined using χ^2 analysis.

C.8.a.2. Efficacy: An important initial consideration will be to identify baseline differences between groups that may have occurred despite the use of urn randomization. The distribution of outcome data will also be examined prior to analysis, to determine the need for transformation and whether parametric analytic methods can be utilized. Successful outcome will be defined in terms of three primary dependent measures: SDs/week, HDDs/week, % of subjects with no HDDs, and % of subjects with non-hazardous drinking (no HDDs and SDs/week <15). Patients will be followed irrespective of whether they continue to receive treatment, so that analysis of both primary drinking measures and secondary outcomes will include all data available for the 12-week treatment period. Data for analyses of drinking outcomes during the 12-week treatment period will come from the daily IVR reports (missing IVR report days which will be coded as the larger of either 5 standard drinks (i.e. a HDD) or the IVR average daily use for the week reporting interval). Analysis of drinking for the 6-month follow-up period will be based on TLFB data collected at each follow-up visit. Secondary outcomes will include mean daily alcohol consumption, %dCDT levels (change relative to baseline), and severity of alcohol-related problems (as measured on the SIP and number of DSM-IV AD criteria).

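### The any-AE comparison is likely to sit near its ceiling and would probably miss a doubled overall side-effect burden; no planned safety test compares the number of AEs per man

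*Combined protocol and SAP*

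**What the plan says.** Section C.8.a.1 sets the form of the safety analysis: "Safety will be analyzed using categorical outcomes, defined by the type and severity of adverse effects". Organ-system summaries are built from the checklist and "will be compared for patients receiving dutasteride or placebo using χ^2 analysis". Three numbered comparisons follow. The first is "the number of patients in each of the two groups who report AEs"; the second is limited to moderate-to-severe AEs, and the third to men who stop treatment because of AEs. Each individual AE seen in at least 5% of either arm is also tested. No comparison uses the number of AEs per man.

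The pilot (C.1.c, Safety) did describe tolerability that way. It gives the "mean number of side effects reported / subject" as 6.0 (SD 5.8) on dutasteride and 8.4 (SD 10.8) on placebo, "during the 8-week medication treatment phase". The trial itself has "a 12-week treatment period". Section C.6.b.3.c says: "Subjects will provide reports of side effects at each bi-weekly phone visit and study visit during the active treatment phase"; the 2-month follow-up is added. Table 1 shows the checklist at three phone calls, five visits (V3-V7), V8 and V9, which is ten occasions per man.

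**The concern.** An any-AE indicator stops recording once a man has reported a single side effect. With pilot averages of six to eight reports over 8 weeks, and a longer trial with repeated checklists, most men in both arms should reach that state. The proportions then have little room to separate, and extra side effects in men who already have one leave no trace.

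Aim 1 hypothesizes that 1 mg/day will be well tolerated. A non-significant any-AE comparison could be taken as support, although it would be the likely result even if overall burden had risen a good deal. The number of effects per man is collected but not analyzed.

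**Working it through.** **The plan's own power figure.** The documents give no power for safety. The efficacy figure in C.8.b (80% for d = 0.45, 80 per arm, α = 0.05) reproduces: 0.45 × √(80/2) = 2.846, and Φ(2.846 − 1.960) = 81%.

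**Inputs.** Pilot means and SDs are from C.1.c. The 176 randomized (C.8.b) give 88 per arm if allocation is equal.

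**Assumptions, not in the documents.** Counts per man are negative binomial, the test is two-sided at 0.05, and the chi-square has no continuity correction.

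**Step 1: dispersion by moments**, k = m² / (SD² − m).
- Dutasteride values: 36 / (33.64 − 6.0) = 1.30
- Placebo values: 70.56 / (116.64 − 8.4) = 0.65

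**Step 2: share with any AE**, 1 − (k/(k+m))^k.

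| Pilot values | Share at pilot mean | Share at doubled mean, same k |
|---|---|---|
| m = 6.0 | 89.4% | 95.2% |
| m = 8.4 | 82.0% | 88.3% |

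**Step 3: power to detect a doubled mean, 88 per arm.** The chi-square figures come from exact enumeration of the 2×2 table, the rank-sum figures from simulation.

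| Pilot values | Any-AE chi-square | Missed | Rank-sum on counts |
|---|---|---|---|
| m = 6.0 | 29% | 71% | about 99% |
| m = 8.4 | 21% | 79% | about 83% |

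For a 50% rise, the any-AE test has about 14% and 11% power, against about 71% and 41% for the rank-sum. With no effect, both tests reject in about 4-5% of trials.

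**Step 4: sensitivity of the any-AE miss rate for a doubling** (88 per arm unless stated).
- 80 per arm: 74-81%
- Yates correction: 81-84%; Fisher: 79-84%
- SD rising in proportion to the mean: 80-83%
- Means scaled by 1.5 to 12 weeks (any-AE share 93% and 86%): 81-82%
- Poisson-lognormal instead of negative binomial: 66-71%

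Across the overdispersed models and choices tried, taking pilot counts at face value, the range is about 66-91%.

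**Step 5: repeat reports.** C.1.c does not say whether one complaint reported at several visits was counted more than once. As an illustration, halve the mean and keep the share of men with no AE fixed. Any-AE power for a doubling rises to about 58% (m = 6.0) and 36% (m = 8.4), so 42-64% are missed. Rank-sum power is then about 100% and 96%.

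**Step 6: the other planned tests.** Under the Step 1 model, assume reports spread evenly over 8 organ systems. At least one organ-system chi-square is then significant after Bonferroni in about 88% (m = 6.0) or 59% (m = 8.4) of trials with a doubled mean. For a single AE, 88 per arm gives 83% power for a rise from 20% to 40%, and 46% for 10% to 20%.

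**The case against.** The strongest reply is that this singles out one of several planned comparisons. C.8.a.1 defines safety by type and severity, and the organ-system, moderate-to-severe, discontinuation and individual-AE tests all remain. Step 6 shows that the organ-system tests alone could catch much of a doubling. This stands. A reader might infer that the safety plan as a whole would miss a doubling 70-80% of the time, and the documents do not support that. Nor do they make the any-AE comparison the headline test or tie Aim 1's tolerability hypothesis to it; it is only listed first.

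Second, dutasteride's documented harms are specific (C.3.a.3), and a total count dilutes them. In the pilot, 7 of 39 randomized men (3 + 4; 18%) reported a sexual side effect. If that share rose from 18% to 36%, each affected man adding one report, a chi-square on that effect has about 77% power. A rank-sum on total counts has 5-7%, little more than the false-positive rate. This also stands, and is why the count should be added rather than substituted. It does not favor the any-AE test, which has only 7-9% power there.

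Third, the 83-99% rank-sum power comes from pilot-type report counts, not from distinct AEs. It is indicative only.

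Fourth, the numbered comparisons follow the organ-system sentence and might be meant within each system, where the ceiling would be weaker. The text does not say so, and the plain reading is any AE.

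Finally, the pilot had fewer reports on dutasteride than on placebo, so a doubling is a test scenario and not a forecast.

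**Conclusion.** The point holds for the any-AE comparison alone. On pilot counts taken as negative binomial, about 82-89% of men would have at least one AE over 8 weeks. With 88 per arm, the comparison would miss a doubled overall burden about 70-80% of the time. The exact rate depends on the assumed distribution and on whether the pilot counted repeats; the illustration in Step 5 brings it to 42-64%. The advantage of counts for detecting a general rise persists in either case.

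The other planned tests may detect much of such a rise, but none summarizes overall burden. A non-significant any-AE result is therefore weak evidence of tolerability. This is an avoidable loss of information in a stated aim and does not make the safety plan as a whole unsound.

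**What to change.** In C.8.a.1:
- Keep all planned comparisons, and report any-AE mainly as a descriptive count per arm.
- Add a between-arm comparison of the number of distinct checklist AEs per man, counting a repeated complaint once. Use a Wilcoxon rank-sum test, or negative binomial regression with log(number of checklists completed) as offset. Report the rate ratio with its 95% CI; the regression supplies this, since the rank-sum test does not.
- State that a non-significant any-AE result will not be read as evidence of tolerability.
- Retain the individual-AE and organ-system tests, because a total count is insensitive to a single specific harm such as sexual effects.

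The cost is analysis-plan wording and minor programming on data already to be collected. A counting rule must be written, including whether the 2-month checklist contributes. The offset treats the count as proportional to the checklists completed, which is only approximate for distinct complaints. No visit or sample size changes.
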